5.2. PHARMACOKINETIC POPULATION

The PK Population will include all subjects who received at least one dose of study drug and have at least one quantifiable PK serum concentration measurement. Subjects will be analyzed according to treatment received in HZNP-TEP-301 study.

6. GENERAL ASPECTS FOR STATISTICAL ANALYSIS

6.1. GENERAL METHODS

The following conventions will be utilized in the analyses:

- In general, descriptive summaries will be provided by treatment received in HZNP-TEP-301 and overall.
- The following treatment group labels will be used: “HZNP-TEP-301 Placebo” for subjects who were randomized to Placebo in HZNP-TEP-301 and “HZNP-TEP-301 HZN-001” for subjects who were randomized to HZN-001 in HZNP-TEP-301.
- Unless otherwise indicated, continuous variables will be summarized using the number of observations (n), mean, standard deviation (SD), median, minimum (min), and maximum (max). Categorical variables will be summarized using number of observations (n), frequency and percentages of subjects.
- The same number of decimal places as the raw data will be presented when reporting min and max, 1 more decimal place than in the raw data will be presented when reporting mean and median, and 2 more decimal places than in the raw data will be presented when reporting SD.
- If multiple assessments occur at a given time point, the latest value will be used. If multiple assessments occur on the same day and the time is not recorded, the average of the values will be used in any descriptive summaries.
- All relevant subject data will be included in listings. All subjects entered into the database will be included in subject data listings.
- Additional programming considerations are provided in Section 14.

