14. Ophthalmic exam: best corrected visual acuity, pupil exam, color vision assessment, Ishihara color plates (or equivalent) or related red desaturation, intraocular pressure, and slit lamp exam. If significant abnormalities are noted compared to previous visits, including a loss of 2 lines or more of vision, development of pupil abnormalities including APD, rise in intraocular pressure, development of corneal infiltrates or other abnormalities not here specified but of concern to the ophthalmologist, further investigations of visual function will be conducted according to the ophthalmologist decision.
15. Vital signs (heart rate, blood pressure, respiratory rate, temperature) will be measured at all clinic visits. Vital signs will be measured pre- and post-infusion on Day 1 and Week 3, and pre-dose on all other infusion days. Additional vital signs will be monitored if infusion-associated AEs occur (see [Section 9.5.4.3](#) for details).
16. Non-diabetic subjects should be fasting at Weeks 1 and 4 only. Diabetic subjects should be fasting at each visit blood glucose is evaluated.
17. ALT/AST must be  $\leq 3$  x the upper limit of normal (ULN) and serum creatinine must be  $< 1.5$  x the ULN (according to age) at the most recent clinic visit to be eligible for enrollment.
18. Subjects must be euthyroid with the baseline disease under control or have mild hypo- or hyperthyroidism (defined as free thyroxine [FT4] and free triiodothyronine [FT3] levels < 50% above or below the normal limits) at the most recent clinic visit. Every effort should be made to correct the mild hypo- or hyperthyroidism promptly and to maintain the euthyroid state for the full duration of the clinical trial.
19. HbA1c must be < 9.0% at the most recent clinic visit. If the HbA1c is elevated and considered clinically significant at any time point after Baseline, it will be repeated approximately every 45 days until it returns to normal or the baseline value.
20. If a sample is positive in the ADA test, after confirmatory and reactive titer testing, the sample will then be tested for NAb. If the subject tests positive for NAb, he/she will be followed until levels either revert to Baseline or the subject's value decreases or remains stable. Any subject with a positive NAb test at Week 48 (or PW) during the Follow-Up Period will continue to be followed until the subject's value decreases or remains stable.

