#### **9.5.4.1.6 Follow-Up of Adverse Events**

Any ongoing study drug-related AE present at the time of study termination, including a clinically significant laboratory test abnormality, will be followed until resolved or until the event stabilizes and the overall clinical outcome has been ascertained.

In the event of unexplained, treatment-emergent, clinically significant abnormal laboratory test results or clinically significant changes in laboratory test results, the tests should be repeated

immediately and followed until the values have returned to within the reference range or to Baseline for that subject.

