6.2.3. Study Baseline and HZN-001 Baseline

The following two definitions of baseline will be utilized for analysis purposes:

- **Study Baseline** will be defined as the last measurement taken prior to first dose in HZNP-TEP-302 (considering unscheduled visits when available). If a Study Baseline value is not obtained in the HZNP-TEP-302 study prior to dosing, the last value measured in HZNP-TEP-301 will be used. Study Baseline comparisons will be provided for all applicable endpoints.
- **HZN-001 Baseline** will be defined as the last measurement taken prior to first dose of HZN-001 whether it occurred in HZNP-TEP-301 or HZNP-TEP-302 (considering unscheduled visits when available). HZN-001 Baseline comparisons will be provided for select assessments of safety, i.e. laboratory assessments, vital signs, ECGs, physical examinations, and ophthalmic examinations.

Change from (Study or HZN-001) Baseline will be defined as the measurement at each time point minus the relevant Baseline value.

The primary objective will be assessed using the Study Baseline.

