6.4. VISIT WINDOWS

All data will be summarized according to the scheduled visit and time points as outlined in the protocol and by the visit denoted on the electronic case report form (eCRF). Further, premature withdrawal (PW) visits (through Week 48/Month 12) will be windowed

to the nearest scheduled visit based on the study day of occurrence relative to the target day of each scheduled visit according to Table 2 below.

Table 2: Visit Windows for Assigning PW Visits to a Scheduled Visit

Study Period	Visit	Target Day	Window for Reassignment to Scheduled Visit
Treatment Period	Day 1	1	1
	Week 1	8	2 - 15
	Week 3	22	16 - 25
	Week 4 (Month 1)	29	26 - 36
	Week 6	43	37 - 53
	Week 9	64	54 - 74
	Week 12 (Month 3)	85	75 - 95
	Week 15	106	96 - 116
	Week 18	127	117 - 137
	Week 21	148	138 - 158
	Week 24 (Month 6)	169	159 - 176
Follow-Up Period	Week 28 (Month 7)	197	177 - 225
	Week 36 (Month 9)	253	226 - 295
	Week 48 (Month 12)	337	≥ 296

In the event that a PW visit gets reassigned to a visit for which the subject has scheduled data collected, the data from the nominal scheduled visit will take precedence and the data from the PW visit will not be summarized.

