6. Perform for female subjects of childbearing potential (including those with an onset of menopause <2 years prior to Screening of HZNP-TEP-301, non-therapy-induced amenorrhea for <12 months prior to Screening of HZNP-TEP-301, or not surgically sterile [absence of ovaries and/or uterus]).

Laboratory results collected in conventional units will be converted to International System of Units (SI) for all summaries and listings. Clinical laboratory test results (hematology, chemistry, thyroid panels, and urinalysis), their changes from Study Baseline, and their changes from HZN-001 Baseline will be summarized by visit and treatment received in HZNP-TEP-301 using descriptive statistics. If a continuous laboratory value is reported as either below or above the limits of quantification, the qualifiers will be dropped and the numeric value used in the analysis (e.g., “< 3” will be summarized as “3” and “> 200” will be summarized as “200”). For hematology, chemistry and thyroid panel, results will be categorized as low, normal, or high based on their normal ranges. For urinalysis tests, results will be classified as normal or abnormal. Results out of range will be identified as such on subject listings. Shift tables for hematology and chemistry panels using categories of low, normal, and high, comparing laboratory test results from

Study Baseline and HZN-001 Baseline to each visit will be presented overall and by treatment received in HZNP-TEP-301 with percentages based on subjects with a non-missing value at Baseline and post-baseline visit. Shift tables for urinalysis results using categories of normal and abnormal, comparing laboratory test results from Study Baseline and HZN-001 Baseline to each visit will be presented overall and by treatment received in HZNP-TEP-301 with percentages based on subjects with a non-missing value at Baseline and post-baseline visit. Additionally, a shift table for glucose by Common Terminology Criteria for Adverse Events (CTCAE) grade and visit will be presented overall and by treatment received in HZNP-TEP-301. Summaries will be provided separately for hyperglycemia and hypoglycemia.

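### The SAP's latest-value rule has no exception for laboratory safety data, so a normal repeat filed under the same visit replaces the abnormal result that prompted it, and no worst post-baseline table is planned

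*SAP*

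**What the plan says.** **Choice of value.** SAP Section 6.1 gives one rule for all analyses: "If multiple assessments occur at a given time point, the latest value will be used". For several values on one day without recorded times, "the average of the values will be used in any descriptive summaries". Neither sentence separates safety from efficacy data.

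**Repeat testing.** Protocol Section 9.5.4.1.6 covers clinically significant laboratory abnormalities that are unexplained and treatment-emergent, and also clinically significant changes. These tests are to be repeated "immediately and followed until the values have returned to within the reference range or to Baseline for that subject". For an elevated HbA1c judged clinically significant, the footnotes to the Schedule of Assessments (Protocol Section 2.1) say "it will be repeated approximately every 45 days until it returns to normal or the baseline value".

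**Visit assignment.** SAP Section 6.4: "All data will be summarized according to the scheduled visit and time points as outlined in the protocol", and by the visit marked on the eCRF. Only premature withdrawal visits are windowed. Unscheduled values are mentioned in the two baseline definitions (SAP Section 6.2.3), but Section 6.4 gives no rule for them after baseline.

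**Laboratory tables.** SAP Section 10.8 plans descriptive summaries by visit, and low/normal/high shift tables for hematology and chemistry that set every visit against both baselines. The glucose CTCAE shift is also by visit. No worst post-baseline laboratory table is described there or indexed in SAP Section 16.

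**The concern.** Each rule is ordinary taken alone. The difficulty is how they combine. A repeat is not a random second reading: it is taken because the first was abnormal, and the sequence ends when the value is in range or back at Baseline. Taking the last value of such a sequence selects on the outcome, and always towards normal.

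The tables exposed are the objective laboratory summaries. They include the glucose grade shift, which bears on hyperglycemia, a named adverse event of special interest. What those tables show would depend partly on which visit label a site gives a repeat, and the SAP does not settle that.

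**Working it through.** **1. Figures to reproduce.** There are none. The documents give no repeat-testing rate, and SAP Section 3.5 says the sample size has no statistical basis. The check is therefore of the rules against each other, with an illustration.

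**2. What the written rules do with a repeat or extra sample.**

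| How it is recorded | What the by-visit table shows | Result |
|---|---|---|
| Same visit, later date or time | The repeat | Abnormal value lost |
| Same visit, same day, no times | The average | Abnormal value diluted |
| Unscheduled, scheduled value abnormal | The scheduled value | Nothing lost at that visit |
| Unscheduled, abnormality seen only at that draw | The scheduled value, or nothing | Abnormality in no laboratory table |
| Under a later scheduled visit of its own | Both values, each at its visit | Nothing lost |

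The third and fourth rows follow the natural reading of SAP Section 6.4, which tabulates by scheduled visit. The SAP does not say so expressly.

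**3. One pair of values.** Assume glucose of 260 mg/dL and then 120 mg/dL under one visit. Protocol Section 9.3.3 gives > 250 mg/dL as its example of severe hyperglycemia.

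- Latest value: 120, so the abnormality disappears.
- Average: (260 + 120)/2 = 190, no longer above 250.
- Worst value: 260, retained.

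**4. Effect on a tabulated rate.** Let q be the true proportion abnormal at a visit and f the share of those with a normal repeat under the same visit. Then

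tabulated rate = q(1 − f), and relative loss = f, whatever q is.

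Further, f = (share repeated) × (share of repeats filed under the same visit) × (share of those that are normal). Each factor is at most 1 and none is given in the documents. For a value of q, borrow 5/43 = 11.6%, the hyperglycemia adverse event proportion in the teprotumumab group of the earlier TED study (Protocol Table 7.2). That is not a per-visit laboratory rate and serves only as a stand-in.

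| f (assumed) | Tabulated rate |
|---|---|
| 0 | 11.6% |
| 0.25 | 8.7% |
| 0.50 | 5.8% |
| 0.75 | 2.9% |
| 1 | 0% |

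A worst-value table would show 11.6% in every row.

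**5. HbA1c.** A repeat 45 days after Week 12 (target day 85 in SAP Section 6.4) falls at about day 85 + 45 = 130. HbA1c is scheduled at Weeks 12 and 24 but not between them. Such a repeat would not normally displace the Week 12 value. The route for HbA1c is the fourth row of the table in step 2; the same-visit route concerns mainly the immediate repeats under Protocol Section 9.5.4.1.6.

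**6. Elsewhere in the SAP.** Section 10.7 keeps vital signs prompted by infusion-associated events out of the descriptive summaries. Section 10.10 counts QTcF threshold crossings at any post-baseline assessment. Laboratory data have neither protection.

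**The case against.** The case against is substantial, and most of it stands as a limit on size.

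- **The trigger is narrow.** The low/normal/high tables count every out-of-range value, but only a subset requires an immediate repeat. This stands and keeps f well below the share of all abnormal results.
- **Glucose fits the trigger poorly.** Protocol Section 9.4.6.3.2 treats raised glucose as a known effect with its own management pathway, so it is hardly unexplained. Glucose is also sampled at every treatment visit, so many rechecks carry their own visit label. This largely stands, although the limb on clinically significant changes could still apply to glucose.
- **Same-visit filing may be uncommon.** Laboratory tests other than urine pregnancy tests go to a central laboratory, so a repeat would normally be drawn on a later date. This is plausible, but the documents do not say how such a repeat is labelled.
- **Other outputs exist.** Clinically significant abnormalities can be reported as adverse events. These are tabulated by maximum intensity, and hyperglycemia has its own AESI search (SAP Sections 10.3 and 10.3.1). Out-of-range listings are planned for each panel. This stands. Those outputs do not use the latest-value rule, but the adverse event tables depend on investigator reporting and do not replace a grade table built from measured values.
- **The study is descriptive, and a worst-value table is a matter of good practice.** No protocol statement is contradicted. Even so, the latest-value rule is a stated choice, and a better one is available at little cost.

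**Conclusion.** The point holds conditionally. Where a repeat shares the visit label of the abnormal result, the written rule puts the later value into the by-visit laboratory tables. Where a sample is unscheduled, an abnormality found only there reaches no laboratory table, on the natural reading of SAP Section 6.4. The relative loss in the first case equals f, anywhere from 0 to 1. The borrowed 11.6% rate and the glucose pair are illustrations, not estimates.

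Three stronger conclusions that a reader might draw are not supported:

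- **That the shift tables are biased towards normal as planned.** If repeats are filed as unscheduled, the abnormal scheduled value remains and there is no such bias from this rule.
- **That abnormal results would survive only in listings.** Events reported as adverse events also reach the adverse event and AESI tables, and the QTcF threshold table counts any post-baseline assessment.
- **That abnormal rates would be roughly halved.** This is just the case f = 0.5, which nothing in the documents singles out.

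The efficacy conclusions are not affected by this point. It is worth correcting because the rule selects on outcome in a predictable direction and the data needed to avoid this are already collected.

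**What to change.** 1. **SAP Section 6.1.** Add that, for laboratory safety data, by-visit tables use the first sample of the scheduled visit, in place of the latest value or the same-day average. Leave the rule unchanged for other data.
2. **SAP Section 6.4 or 10.8.** State that repeat and unscheduled post-baseline samples stay out of by-visit tables but enter the worst-value table below.
3. **SAP Sections 10.8 and 16.** Add a shift from baseline to the worst post-baseline value, including repeats and unscheduled samples. At minimum do this for glucose CTCAE grade, with hyperglycemia and hypoglycemia kept separate as already planned. Preferably do it for each panel, with the lowest and highest values taken separately where both directions matter.

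The worst-value table should sit beside the by-visit tables, since subjects sampled more often have more chances of an extreme value. The cost is one changed sentence, one clarification and a few extra tables, with no new data collection.

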6.2. KEY DEFINITIONS

6.2.1. Study Eye

The "study eye" (i.e., most severely affected eye) will remain the same as that identified at the Baseline (Day 1) Visit of Study HZNP-TEP-301. Both eyes will be assessed for efficacy but the study eye will be used to assess the primary outcome measure.

6.2.2. Fellow Eye

The non-study eye will be referred to as the “fellow eye”.

6.2.3. Study Baseline and HZN-001 Baseline

The following two definitions of baseline will be utilized for analysis purposes:

- **Study Baseline** will be defined as the last measurement taken prior to first dose in HZNP-TEP-302 (considering unscheduled visits when available). If a Study Baseline value is not obtained in the HZNP-TEP-302 study prior to dosing, the last value measured in HZNP-TEP-301 will be used. Study Baseline comparisons will be provided for all applicable endpoints.
- **HZN-001 Baseline** will be defined as the last measurement taken prior to first dose of HZN-001 whether it occurred in HZNP-TEP-301 or HZNP-TEP-302 (considering unscheduled visits when available). HZN-001 Baseline comparisons will be provided for select assessments of safety, i.e. laboratory assessments, vital signs, ECGs, physical examinations, and ophthalmic examinations.

Change from (Study or HZN-001) Baseline will be defined as the measurement at each time point minus the relevant Baseline value.

The primary objective will be assessed using the Study Baseline.

6.2.4. Study Day and HZN-001 Study Day

The following two definitions of study day will be utilized:

- **Study Day:** For assessments on or after the date of treatment start in HZNP-TEP-302, Study Day will be calculated as assessment date - first dose date in HZNP-TEP-302 + 1. For assessments prior to dosing in HZNP-TEP-302, Study Day will be calculated as assessment date - treatment start date in HZNP-TEP-302. Further, there will be no Study Day 0. Study Day will appear in all relevant listings in which a date is provided (e.g. visit date, assessment date, and start/stop dates of events).
- **HZN-001 Study Day:** For assessments on or after the date of HZN-001 treatment start (regardless of whether HZN-001 was initiated in HZNP-TEP-301 or HZNP-TEP-302), HZN-001 Study Day will be calculated as assessment date - first dose date of HZN-001 + 1. For assessments prior to HZN-001 treatment start, HZN-001 Study Day will be calculated as assessment date - HZN-001 treatment start date. Further, there will be no HZN-001 Study Day 0. HZN-001 Study Day will appear in listings of safety data, i.e. laboratory assessments, vital signs, ECGs, physical examinations, and ophthalmic examinations.

6.3. MISSING DATA

6.3.1. Birth Dates

If the date of birth is only partially available, the first of the month will be imputed for any missing days and January will be imputed for any missing months. Imputed dates will not be presented in the data listings.

6.3.2. Medical History Diagnosis Dates

If the onset date of Graves' disease or TED is only partially available, the first of the month will be imputed for any missing days and January will be imputed for any missing months. Imputed dates will not be presented in the data listings.

6.3.3. Medication Dates

For prior and concomitant medications with incomplete dates, the following rules will be used to impute start and/or stop dates for the purposes of determining if a medication is prior or concomitant only. Imputed dates will not be presented in the data listings.

For partial start dates:

- If day is missing, and the month and year match the month and the year of the first dose date, the day of the first dose date will be imputed. Otherwise, the first of the month will be used.
- If day and month are missing and the year matches the year of the first dose date, the month and the day of the first dose date will be imputed. Otherwise, 01 January will be used.
- If the start date is completely missing, the start date will not be imputed. If the stop date is after first dose date, the medication will be considered to be both prior and concomitant. If the stop date is prior to the first dose date, the medication will be considered to be prior only. If the stop date is after the first dose date but prior to the last dose date + 21 days, the medication will be considered prior and concomitant during the Treatment Period only. If the stop date is after the last dose date + 21 days, the medication will be considered prior and concomitant during both the Treatment Period and Follow-Up Period.
- If the stop date is complete and the imputed start date is after the actual stop date, then the start date will be imputed as the stop date.

For partial stop dates:

- For stop dates, if the day is missing, then the last day of the month will be used.
- If the month is missing, then December will be used.
- If the stop date is completely missing then the date of last study visit will be used.

6.3.4. Adverse Events

For adverse events with incomplete dates, the following rules will be used to impute start and/or stop dates for the sole purpose of determining if an AE is treatment-emergent. Imputed dates will not appear in the data listings.

For partial start dates:

- If day is missing, and the month and year match the month and the year of the first dose date, the day of the first dose date will be imputed and the AE will be considered treatment-emergent. Otherwise, the first of the month will be used and the treatment-emergent status will be assessed relative to the dosing start date.
- If the day and month are missing, and the year matches the year of the first dose date, the month and the day of the first dose date will be imputed, and the AE will be considered treatment-emergent. Otherwise, 01 January will be used and the treatment-emergent status will be assessed relative to the dosing start date.
- If the start date is completely missing, the AE will be considered treatment-emergent unless the stop date is complete and prior to the first dose or provides enough partial information to rule out a treatment-emergent status.
- If the stop date is complete and the imputed start date is after the actual stop date, then the start date will be imputed as the stop date and the treatment-emergent status will be assessed relative to the dosing start date.

Any missing intensity assessments for AEs will be imputed as “severe” and any missing relationship to study drug will be considered “related” for summary purposes.

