#### **9.5.4.1.2 Documentation of Adverse Events**

Adverse events that are ongoing at the completion of HZNP-TEP-301 and/or occur prior to dosing on Day 1 will be considered pre-dose AEs. The TEAE reporting period begins with administration of the first dose of study medication on Day 1 and continues until 3 weeks after the last dose of study drug, and the Follow-Up AE reporting period begins 3 weeks after the last dose of study drug through completion of the Follow-Up Period (Month 12 or PW). All pre-dose AEs, TEAEs, and AEs during the Follow-Up Period must be recorded in the source documents and in the subject's eCRF.

If the Investigator observes an SAE after study completion that he/she believes was possibly caused by the study medication, the Investigator will report this SAE using the procedures described in [Section 9.5.4.1.5](#).

Detailed information regarding all SAEs must also be recorded on the Serious Adverse Event Reporting Form. Whenever possible, the Investigator should group together into a single term the signs and symptoms that constitute a single diagnosis. For example, cough, rhinitis, and sneezing might be grouped together as "upper respiratory infection" if the Investigator is confident of the diagnosis.

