15. Vital signs (heart rate, blood pressure, respiratory rate, temperature) will be measured at all clinic visits. Vital signs will be measured pre- and post-infusion on Day 1 and Week 3, and pre-dose on all other infusion days. Additional vital signs will be monitored if infusion-associated AEs occur.
16. Non-diabetic subjects should be fasting at Weeks 1 and 4 only. Diabetic subjects should be fasting at each visit blood glucose is evaluated.
17. ALT/AST must be ≤ 3 x the upper limit of normal (ULN) and serum creatinine must be < 1.5 x the ULN (according to age) at the most recent clinic visit to be eligible for enrollment.
18. Subjects must be euthyroid with the baseline disease under control or have mild hypo- or hyperthyroidism (defined as free thyroxine [FT4] and free triiodothyronine [FT3] levels $< 50\%$ above or below the normal limits) at the most recent clinic visit. Every effort should be made to correct the mild hypo- or hyperthyroidism promptly and to maintain the euthyroid state for the full duration of the clinical trial.
19. HbA1c must be $< 9.0\%$ at the most recent clinic visit. If the HbA1c is elevated and considered clinically significant at any time point after Baseline, it will be repeated approximately every 45 days until it returns to normal or the baseline value.
20. If a sample is positive in the ADA test, after confirmatory and reactive titer testing, the sample will then be tested for NAb. If the subject tests positive for NAb, he/she will be followed until levels either revert to Baseline or the subject's value decreases or remains stable. Any subject with a positive NAb test at Week 48 (or PW) during the Follow-Up Period will continue to be followed until the subject's value decreases or remains stable.
21. Not collected for subjects who prematurely discontinue from the open-label Treatment Period.
22. Adverse events that are ongoing at completion of HZNP-TEP-301 and/or occur prior to dosing on Day 1 will be considered pre-dose AEs. Adverse events occurring or worsening after the dose on Day 1 through the end of the Treatment Period will be considered treatment-emergent AEs (TEAEs). Adverse events occurring or worsening during the Follow-Up Period will be considered postdose AEs. All SAEs that occur from the signing of informed consent through 30 days after study discontinuation will be recorded.

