10.3. ADVERSE EVENTS

All adverse events will be coded using MedDRA version 20.1. The TEAE reporting period begins with administration of the first dose of study medication on HZNP-TEP-302 Day 1 and continues until 3 weeks (21 days) after the last dose of study drug. The Follow-Up AE reporting period begins 3 weeks (21 days) after the last dose of study drug through completion of the Follow-Up Period (Week 48 or PW).

Missing data conventions for AEs are described in Section 6.3.4.

An overall summary of TEAEs will be provided by treatment received in HZNP-TEP-301 and overall, including the number and percentage of subjects with each AE type as well as the number of events for each of the following:

- TEAEs

- Serious TEAEs
- Related TEAEs
- Related serious TEAEs
- TEAEs with an intensity of severe or higher
- TEAEs leading to interruption of study drug administration
- TEAEs leading to permanent withdrawal of study drug
- Related TEAEs leading to permanent withdrawal of study drug
- TEAEs leading to study discontinuation
- Related TEAEs leading to study discontinuation
- TEAEs leading to death

Additional TEAE summaries will be provided by treatment received in HZNP-TEP-301 and overall, including the number and percentage of subjects experiencing TEAEs for the following:

- TEAEs overall and by SOC and PT, including the following subgroup analyses:
 - Age (<65 years, ≥65 years)
 - Gender (male, female)
 - Race (white, black or African American, Asian, other)
 - Ethnicity (Hispanic or Latino, not Hispanic or Latino)
- Related TEAEs overall and by SOC and PT
- TEAEs by maximum intensity, overall and by SOC and PT
- Serious TEAEs, overall and by SOC and PT
- Related TEAEs by intensity, overall and by SOC and PT
- TEAEs leading to permanent withdrawal of study drug, overall and by SOC and PT

- TEAEs of special interest including potential infusion-related reaction, anaphylactic reaction, hearing loss, hyperglycemia, muscle spasm, and diarrhea (see Section 10.3.1), by SOC, PT and overall
- TEAEs of special interest with missing AE start times including potential infusion-related reaction of any type, infusion-related reaction excluding those of an anaphylactic nature, and anaphylactic reactions (see Section 10.3.1), by SOC, PT and overall

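### For AEs with incomplete start dates, SAP 6.3.4 as written labels some AEs known to be pre-dose, and on a literal reading some known Follow-Up AEs, as treatment-emergent, against the plan's own period definitions

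*SAP*

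**What the plan says.** **Definitions.** SAP 3.8, Table 1, footnote 22: "Adverse events that are ongoing at completion of HZNP-TEP-301 and/or occur prior to dosing on Day 1 will be considered pre-dose AEs". The same footnote makes an AE that worsens after the Day 1 dose a TEAE, and one that arises or worsens during Follow-Up a postdose AE. Protocol 9.5.4.1.2 repeats the pre-dose definition and adds that "All pre-dose AEs, TEAEs, and AEs during the Follow-Up Period must be recorded in the source documents" and in the eCRF, so carried-over AEs are in the data on which the rule acts.

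SAP 10.3: "The TEAE reporting period begins with administration of the first dose of study medication on HZNP-TEP-302 Day 1" and it "continues until 3 weeks (21 days) after the last dose of study drug". The Follow-Up AE period starts at that point. For missing dates, 10.3 refers the reader to 6.3.4.

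**Rule for incomplete start dates (SAP 6.3.4).**
- Day missing, month and year equal to those of first dose: "the day of the first dose date will be imputed and the AE will be considered treatment-emergent".
- Day and month missing, year equal to that of first dose: "the month and the day of the first dose date will be imputed, and the AE will be considered treatment-emergent".
- No match: impute the first of the month (or 1 January), and "the first of the month will be used and the treatment-emergent status will be assessed relative to the dosing start date".
- Start wholly missing: "the AE will be considered treatment-emergent unless the stop date is complete and prior to the first dose", or a partial stop date excludes it.
- If the stop date is complete and the imputed start falls after it, the start is set to the stop date and status is then judged against dosing start.

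**The concern.** In an extension study the lead-in AEs lie directly before Day 1, and those still ongoing are carried into the new AE data. If an incomplete date turns a carried-over AE into a TEAE, a lead-in event is counted against the extension infusions; in the group that already received teprotumumab in HZNP-TEP-301, it could be an effect of the earlier course. At the other end, calling a Follow-Up AE treatment-emergent puts it in the wrong set of tables. The Treatment Period and Follow-Up AE summaries are separate, and the Follow-Up ones have their own denominator.

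These are two faults with two causes, so one edit does not cure both.

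**Working it through.** The documents give no figure for this point, so there is none to reproduce. The check runs the rule on dates and then estimates how often it would bite.

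**Inputs.** Last dose at Week 21, target Day 148 (SAP 6.4, Table 2). TEAE period ends at last dose + 21 days (SAP 10.3). Day 1 falls within 14 days after the final lead-in visit, which is Week 24 for non-responders and up to Week 72 for relapsers (SAP 3.4). SAP 6.3.4 does not say which study its first dose date belongs to; HZNP-TEP-302 is inferred from 10.3.

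**Example.** Day 1 = 20 Nov 2018. Last dose = 20 Nov 2018 + 147 days = 16 Apr 2019. End of TEAE period = 16 Apr + 21 days = 7 May 2019.

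| AE as recorded | Start imputed by 6.3.4 | Label under 6.3.4 | Label under the definitions |
|---|---|---|---|
| Ongoing from lead-in, start 2018 | 20 Nov 2018 | TEAE | Pre-dose |
| Ongoing from lead-in, start Nov 2018 | 20 Nov 2018 | TEAE | Pre-dose |
| Ongoing from lead-in, start unknown, no stop date | none | TEAE | Pre-dose |
| Start Nov 2018, stopped 18 Nov 2018 | 18 Nov 2018 (the stop date) | Pre-dose | Pre-dose |
| From lead-in, start Oct 2018 | 1 Oct 2018 | Pre-dose | Pre-dose |
| Start Aug 2019 | 1 Aug 2019 | TEAE, read literally | Follow-Up |
| Start May 2019 | 1 May 2019 | TEAE | Either (period ends 7 May) |

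Rows 1 to 3 are the lead-in fault. It comes from the match rules and the wholly-missing rule. Row 4 shows that a complete stop date before first dose already rescues an AE, so the fault concerns mainly AEs that continue past Day 1. Row 5 shows that the no-match branch handles earlier-month lead-in AEs correctly. Row 6 is the Follow-Up fault: 1 Aug 2019 is 107 days after the last dose and 107 − 21 = 86 days after the period ended, yet it is after dosing start, the only reference point named. Row 7 is truly ambiguous, and TEAE is a reasonable label.

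**Illustrative share of carried-over AEs that would match first dose.** Assumptions: Day 1 uniform over a calendar year, and onset uniform over the lead-in. The ranges span a gap of 0-14 days before Day 1 and no gap.

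| Onset spread over | Day missing: same month as Day 1 | Only year known: same year as Day 1 |
|---|---|---|
| 24 weeks (168 days) | 5.3% (gap) to 8.8% (no gap) | 75% to 76.8% |
| 72 weeks (504 days) | 1.8% to 2.9% | 35% to 36% |

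**Follow-Up AEs** (onset uniform over Days 170 to 337, all doses on target days):

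| Reading of the no-match branch | Day missing: called TEAE | Only year known: called TEAE |
|---|---|---|
| Literal, dosing start only | 100% | 100% |
| With the 10.3 end applied to the imputed date | 8.8% | 76.8% |

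The known date parts therefore exclude a TEAE in 100 − 8.8 = 91.2% of day-missing cases and 100 − 76.8 = 23.2% of year-only cases. The rest share a month or year with the TEAE period and stay ambiguous. The end bound leaves the lead-in shares unchanged.

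**The case against.** The strongest defence has four parts.

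1. Footnote 22 classes an AE as pre-dose by its recorded status, which needs no onset date, so it can be applied before 6.3.4. This is plausible, but no order of precedence is stated, and 6.3.4 says without exception that the matching AE is treatment-emergent.

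2. The end of the TEAE period in 10.3 and the separate Follow-Up tables in the SAP's table index imply an end bound without saying so. A programmer may well apply it. But 6.3.4 does not say so, while the neighbouring medication rule in 6.3.3 does name last dose + 21 days. Two programmers could produce different tables from the same text.

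3. Resolving doubt toward treatment-emergent is a common conservative convention, and 6.3.4 treats missing intensity and missing relationship in the same spirit. This stands for ambiguous dates. It does not cover cases where the recorded status or the known date parts already exclude a TEAE.

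4. The effect is probably small. AEs are assessed at every clinic visit, so year-only starts should be uncommon, and the analysis is descriptive with no test to distort. This stands, and it limits the severity.

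A reader might go further and infer that testing against dosing start is what mislabels lead-in AEs. It is not: that branch gives the right answer for them. A reader might also infer that the Follow-Up tables are certainly understated. The SAP nowhere says that an AE labelled treatment-emergent is removed from those tables, so that consequence is not established.

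**Conclusion.** Wrong as written; minor. Followed to the letter, SAP 6.3.4 contradicts footnote 22 and Protocol 9.5.4.1.2 for carried-over AEs. On the literal reading it also contradicts SAP 10.3 for AEs known to lie in Follow-Up.

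Only AEs with incomplete start dates are affected, and their number is not given. The percentages above are shares of such AEs under uniform onset, not of all AEs. The 75-77% applies only to year-only dates in subjects entering at Week 24; for day-missing dates the share is 5-9% at most. The Follow-Up part mainly concerns HZNP-TEP-301 proptosis non-responders, who alone enter the Follow-Up Period. The direction is over-counting of TEAEs, not concealment. For scale, if a treatment column held 20 to 40 subjects (an assumption; the documents give no size), one misplaced subject would move a preferred-term rate by 1/40 = 2.5 to 1/20 = 5 percentage points.

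The documents do not support a claim that the TEAE tables are materially inflated.

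**What to change.** Make two changes in SAP 6.3.4.

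(a) Place this before the imputation rules: an AE recorded as ongoing at HZNP-TEP-301 completion, or otherwise known to have begun before Day 1 dosing, is a pre-dose AE whatever its imputed date, unless it is recorded as worsening after Day 1 dosing.

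(b) Judge status against both the start and the end (last dose + 21 days) of the TEAE period in Section 10.3. If the known date parts place the AE wholly after that end, class it as a Follow-Up AE; if they allow either period, keep it as a TEAE.

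It would also help to state that the first dose date in 6.3.4 is the one in HZNP-TEP-302. The cost is a few lines of SAP text and a small programming change, with no new data and no change to study conduct. The conservative label remains wherever the date is truly uncertain.
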